9.3 Data Management

Study-collected data will be stored “centrally” on a secure UW DFMCH server. These data will be accessible locally or remotely to authorized research team members in Madison, Hershey, Boston and Salt Lake who will be able to view and/or enter data. Data provided online by the study participants will be “deposited” directly into the UW DFMCH-housed RedCap database, with required response to all questions, ensuring data are complete and updated in a timely manner. The REDCap database will be developed and managed by a UW database administrator experienced with the proposed methods.^{17,46-48} Data from the in-person or virtual assessment sessions (at baseline and exit) and follow-up data collected online or by a trained researcher by phone will be recorded by the researcher through the participant’s web link; or “on paper,” prior to being entered by a research staff into the outcome database. All visits will be encouraged to be completed via electronic web link, regardless of meeting in-person or remotely, however phone / paper completion will be an option. The participant will be encouraged to access the web-link during their initial study visit, so they can have practice with the web-link surveys prior to completing them remotely on their own. Outcome data, labeled by the subject’s study ID only, will be stored in an outcome database, separate from the identifiable data, used for subject tracking. If data on the prescribed opioids are extracted by a database analyst from the EHR, the UW database analyst will ensure standardized extraction of EHR data across the health systems and will facilitate linking of de-identified EHR data to other outcome data. The videorecorded activity and in-depth qualitative interviews will be stored on a secure UW server and managed by the UW Information Technology team.

9.4 Data Monitoring

Data and Safety Monitoring Plan Prior to the subject enrollment, a detailed data/safety monitoring plan will be submitted to the IRB and the PCORI for approval. Although we do not anticipate serious adverse events (see item 3), should any occur, the site PI will report it to the Research Subjects Advocate and the IRB and the Project Officer at the PCORI within 48 hours, using the subject ID number. Annual reports of adverse events will be submitted to the PCORI. The data and safety monitoring will be provided through the regular study team meetings and by the Data and Safety Monitoring Committee (DSMC).

Data and Safety Monitoring Committee The PI’s prior RCTs evaluating MM intervention for opioid-treated CLBP and for alcohol dependence were both considered to be of “minimal risk” by the UW IRB.^{17,46-48} Therefore, an independent Data and Safety Monitoring Board and an interim data analysis are not expected to be required. However, to maximize participant safety, and the validity and integrity of the data, we will form a DSMC, which we successfully implemented in our prior similar trials.^{17,46-48} This committee will include 4 individuals who are not involved in the trial as investigators or research staff: two clinicians ([name]; [name], LCSW, MSW, MDiv, MA); patient stakeholder and advocate ([name], member of the Community Advisors on Research Design and Strategies (CARDS); and a statistician ([name]; Director, Statistical Data Analysis Center, University of Wisconsin-Madison– Chair of the DSMC). During the course of the study, the DSMC will meet twice a year for data and safety monitoring, and to approve continuation of the study protocol. Details of the DSMC operations and procedures are described in the Data Safety and Monitoring Plan and DSMC Charter document (see Appendix).

Study Team Meetings The study team meetings will be scheduled on a regular basis and will include Site Manager Meetings, and regular Site Team Meetings. A plan for communication within and between sites will be established and included in the Manual of Operations. The Investigator Meetings will be led by the study or site PIs, or the study

manager, with meetings scheduled on average every 1-2 months, will follow a written agenda and produce meeting minutes. The Investigator Meetings will invite participation of all Investigators, consultants, the study manager and site managers, and other team members.

Annual Site Visits The Study Manager and/or PI will conduct a site visit each site 1-2 times per year to monitor and ensure compliance with the study protocol and data integrity. Site visits will include monitoring/auditing of protocol compliance, study procedures, safety and related reporting, regulatory and other study documents, and random sampling of data collected. A report of visit results will be generated and sent to the Study PI, Site PI, and Site Manager for the audited site.

10 Assessment of Safety

10.1.1 Definition of an Adverse Event (AE)

We will report Adverse event means any untoward medical occurrence associated with the use of an intervention in humans, whether or not considered intervention-related (21 CFR 312.32 (a)).

10.1.2 Definition of a Serious Adverse Event (SAE)

A Serious Adverse Event is any of the following:

- Fatal;
- Life-threatening;
- Persistent or significantly disabling or incapacitating;
- An inpatient hospitalization or prolongation of hospitalization;
- A congenital anomaly or defect; OR
- A significant medical incident that, based upon appropriate medical judgement, may jeopardize the participant and requires medical or surgical intervention to prevent one of the outcomes listed above

10.1.3 Definition of an Unanticipated Problem (UP)

An Unanticipated Problem is an event that meets all of the following criteria:

- Is more likely than not related to the research;
- Negatively affects the risk/benefit ratio of the research (this includes physical as well as psychosocial risks); AND
- Was not described in the protocol, Investigator's Brochure, IRB application, or informed consent document OR exceeds the specificity, frequency, or severity described in these documents

10.2 Classification of an Adverse Event

10.2.1 Severity of Event

All AEs will be assessed by the clinician using the below grading system. For AEs not included in the protocol defined grading system, the following guidelines will be used to describe severity.

Mild – Events require minimal or no treatment and do not interfere with the participant's daily activities.

Moderate – Events result in a low level of inconvenience or concern with the therapeutic measures. Moderate events may cause some interference with functioning.

Severe – Events interrupt a participant's usual daily activity and may require systemic drug therapy or other treatment. Severe events are usually potentially life-threatening or incapacitating.

Life-Threatening – Events that result in life threatening consequences, and urgent intervention is indicated.

Death – Events that result in death.

10.2.2 Relationship to Study Agent

For all collected AEs, the clinician will determine the AE's causality based on temporal relationship and his/her clinical judgment. The degree of certainty about causality will be graded using the categories below.

Definite – There is clear evidence to suggest a causal relationship, and other possible contributing factors can be ruled out. The clinical event occurs in a plausible time relationship to the study intervention and cannot be explained by concurrent disease or other interventions, drugs or chemicals.

Probable – There is evidence to suggest a causal relationship, and the influence of other factors is unlikely. The clinical event occurs within a reasonable time after the study intervention, is unlikely to be attributed to concurrent disease or other the study interventions, drugs or chemicals.

Possible – There is some evidence to suggest a causal relationship (e.g., the event occurred within a reasonable time after the study intervention). However, other factors may have contributed to the event (e.g., the participant's clinical condition, other concomitant events). Although an AE may rate only as "possibly related" soon after discovery, it can be flagged as requiring more information and later be upgraded to "probably related" or "definitely related," as appropriate.

Unlikely – A clinical event whose temporal relationship to the study intervention makes a causal relationship improbable and in which other interventions, drugs or chemicals or underlying disease provides plausible explanations (e.g., the participant's clinical condition, other concomitant treatments).

Unrelated – The AE is completely independent of the study intervention, and/or evidence exists that the event is definitely related to another etiology. There must be an alternative, definitive etiology documented by the clinician.

10.2.3 Expectedness

The Principal Investigator or other delegated PI will be responsible for determining whether an AE is expected or unexpected. An AE will be considered unexpected if the nature, severity, or frequency of the event is not consistent with the risk information previously described for the study agent.

10.3 Time period and frequency for event assessment and follow-up

Monitoring for AEs, including UPs and SAEs, will be conducted by the study team at each of the assessment visits and other contact times. Any medical or mental health condition that is present at the time that the participant is screened will be considered as baseline and not reported as an AE. Participants will be asked if they experienced any potential side effects related to their participation in the study. AEs will be further assessed at the assessment sessions by the Short Opioid Withdrawal Scale. Any AE occurring any time after informed consent is obtained will be reported to the study or site PI, with SAEs reported immediately (or as soon as possible if the situation does not allow for immediate reporting). AEs/UPs and SAEs will be recorded by research staff on an ICTR's Adverse Events tracking log, and entered into the study database. See Section 10.4 for the timeline of reporting of AEs/UPs/SAEs.

10.4.1 Events of special interest

N/A

10.4.2 Reporting of pregnancy

Although we will not enroll women who report pregnancy, and later on do not obtain laboratory testing toward pregnancy, if a female participant reports pregnancy after the enrollment, we will discuss this situation with the DSMC to make a determination about further participation on a case by case basis.

10.5 Study Halting Rules

While the study interventions and procedures are minimal risk and not expected to produce any unanticipated serious adverse events, the study may be halted or temporarily suspended if it is discovered that the interventions pose a serious consistent life- or health-threatening risk to participants. Should SAEs occur, the DSMC and other study oversight agencies will be involved in a timely manner as specified above to determine further course of action.

10.6 Safety Oversight

Our Data Safety and Monitoring Committee (DSMC) will provide Safety Oversight. See Section 9.4.

11 Study Monitoring, Auditing, and Inspecting

11.1 Medical/Safety Monitoring

Safety protocol will be implemented by a trained researcher or therapist in case of presence of any worrisome symptoms, including inappropriate behavior during the study sessions or assessments. In case of worrisome symptoms during the intervention or assessment sessions, regardless of their mode of delivery (ie, in person, by phone, or via online platforms), a therapist or a research staff will discuss the concerns individually with the symptomatic participant, follow the Safety Protocol procedures, and call the study clinician as needed if concerns persist for further assessment and directions (see Section 2.5.2 for details). For those who are experiencing mental health problems, information on the resources available for counseling or other services to help with anxiety, distress, or feelings of sadness, will be provided. Depending on clinician's assessment, participants will be cleared to stay at home or go home (by themselves, with a family member or a friend, or via study-provided cab) or referred to the appropriate further assessment, including in the Emergency Department (ED) if needed. Participants who are excused from the assessment meeting will be asked to reschedule it; however, they will not be able to reschedule a missed intervention session. In case of emergency, the therapist or research staff will call hospital security or 911.

At each assessment session (baseline, 3, 6, 9, 12 months) participants will be screened for an intent to self-harm through their answers to item 5 on the existing outcome measure, the Current Opioid Misuse Measure (COMM): *"In the past 30 days, how often have you seriously thought about hurting yourself?"* (with responses ranging from 0=Never, 1=Seldom, 2=Sometimes, 3=Often, to 4=Very Often). Scores 3 (Often) and 4 (Very Often) will be considered a "positive screen" and trigger the research staff to initiate the Safety Protocol, which includes involving the designated study clinician for assessment of the participant's intent to harm and disposition. Depending on clinician's assessment, participants will be "cleared" or referred for appropriate further assessment, including in the Emergency Department (ED), if needed. All participants assessed by the study clinician will be provided information on the local resources available for counseling or other mental health services. COMM responses are monitored by the research staff during business hours.

If the Safety Protocol is implemented, the assessed participants will be encouraged to contact their regular providers for evaluation, if needed, and will receive a follow-up phone call from the study site clinician the following day, if needed. Notification of participant's regular provider or a designated emergency contact person will not be required unless an ED assessment is necessary. Participants who are excused from the assessment session will be asked to reschedule it; however, they will not be able to reschedule a missed intervention session. They will be encouraged to continue study activities. In case of ED referral, the site PI or designated study clinician will notify the receiving physician in the ED, participant's regular provider and the emergency contact person (this procedure is outlined in the consent/HIPAA form).

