Drs. [name], [name] (Madison, WI); [name], [name] (Boston, MA); [name], [name] (Hershey, PA) are physicians; [name] (Madison, WI) is a Nurse Practitioner; Drs. [name], [name], (Boston, MA), and [name] (Salt Lake City, UT) are clinicians practicing in the fields of mental health. All the above Investigators are experienced in the management of issues related to the treatment of CLBP and mental health problems including acute suicidality. In addition, [name] (Salt Lake City, UT) and [name] (Madison, WI) have expertise in physiotherapy for CLBP. Together, the above Investigators as well as the study therapists and other designated study clinicians will be able to address any medical or mental health issues that may arise. A designated 'on call' study physician will always be readily available via cell phone or pager for study-related questions or problems; a designated 'on call' mental health specialist will be able to address mental health related issues, including acute suicidality. A study clinician will always be consulted if the Safety Protocol is initiated (see Appendix). The Safety Protocol has been successfully utilized in the PI's prior studies. The data safety monitoring committee (DSMC) and the IRB will be timely notified in the case of a serious adverse event.

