- During virtual study sessions, the study staff present for the sessions will engage in the session in a private location, with headphones/earbuds, and will turn off other devices as to protect confidentiality.
- During virtual study sessions, the videorecorded activity will be recorded using the institutionally-approved HIPAA-compliant virtual platform; after the session, it will be transferred to and stored at the secure UW servers.
- During the intervention sessions, the therapist and the research staff will moderate the session to ensure that only study participants are present for both virtual and in-person sessions.
- Collection of sensitive information about participants is limited to the amount necessary to achieve the aims of the research.
- All of the data related to study participation will be kept confidential; data will be coded with a unique code for each participant and stripped of identifiers prior to being viewed by Investigators.
- Electronic outcome data will be managed using the secure REDCap database.
- Experienced EHR data analyst will help link the EHR data on prescribed opioids to other outcome data in a way that does not compromise participant confidentiality, using a study ID number for all data linkages.
- A master list with identifiers will be kept in a separate secure database/separate locked filing cabinet, by the Site PI or Site Manager at the site's research office.
- Identifying information will not be recorded on any outcome measures/data.
- All patient identifying data will be destroyed after the trial is completed, per IRB guidance.
- All computerized data will be password-protected and personnel will be restricted to viewing only data appropriate to their role in the project; all study personnel will receive the training required by the IRB.
- Outcome data will NOT become a part of the participant medical record; all data will be collected for research purposes only.

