For those screened but not enrolled in the study, all identifiable information will be destroyed. We will retain non-identifiable information collected during the screening process to help determine main reasons for ineligibility or declining participation and inform future research. All potential subjects will provide verbal consent for obtaining these data at the beginning of their screening process.

7.2.2 Follow up:

Table 4. Acceptable Window for Study Visits (including weekends)

| Visit | Window | Activities |
|---|--|--|
| Initial Visit (Screening, Enrollment, Baseline Assessment, Randomization) | + up to 12 weeks from the last contact / screening | Virtual or in-person visit. Confirm eligibility; consent/HIPAA authorization form; enrollment; completion of baseline questionnaires and videorecorded activity; randomization; scheduling for the intervention; compensation. |
| 3-month follow-up | + up to 8 weeks from due date | Online/phone/mail (if necessary) questionnaires, compensation mailed |
| 6-month follow-up | + up to 8 weeks from due date | Online/phone/mail (if necessary) questionnaires, compensation mailed |
| 9-month follow-up | + up to 8 weeks from due date | Online/phone/mail (if necessary) questionnaires, compensation mailed |
| 12- month follow-up (exit) | + up to 16 weeks from due date | Virtual or in-person visit. Completion of exit questionnaires and videorecorded activity, compensation. Completion by phone or mail if necessary. |
| In-depth qualitative interview (subset of 80 participants) | + up to 16 weeks from due date | Qualitative interview by phone; compensation mailed. |

The final study visit, the “Exit Visit”, will occur approximately 12 months from the intervention start date for a given participant (Table 4). A subset of participants who completed the final study visit will be invited to undergo an in-depth qualitative interview by phone about their experience with the study intervention and its effects (Table 4).

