the participant is not able or willing to provide data via online system, s/he will have an option to complete these surveys “on paper” or online or by phone with the assistance from the researcher. Follow-up surveys (at 3, 6, and 9-months) will be completed online and by phone, and check-ins (approximately every 2-4 weeks) will be conducted per participant communication preference. For surveys completed online, each participant will follow a unique web link (emailed to each participant at the time of follow-up) that will allow answering survey questions online. The online responses will be entered by the participant directly into the DFMCH-housed secure REDCap database using a participant-specific web link. At follow-up, those who prefer to provide data by phone will be called by the study coordinator who will mark the participant responses “on paper” or enter directly into the electronic database. Data collected “on paper” (e.g. because of participant preference; as a result of a phone interview; due to computer malfunction; data on prescribed opioids extracted from participant electronic health record) will be labeled with participant ID only, entered into the REDCap database by a research staff member and stored in a separate locked filing cabinet. Only participant ID will be linked to the participant outcome data stored in the REDCap database.

Participant videorecorded data will be uploaded to the UW DFMCH secure storage system via a web-based interface. During virtual study sessions, the videorecorded activity (interview portion) will be recorded using the institutionally-approved HIPAA-compliant virtual platform; after the session, it will be transferred to the UW DFMCH secure storage system. Security will be provided by utilizing Secure Shell (SSH) with shared/private-key encryption on all connections to and from the DFMCH storage system. Additionally, security and identify verification will be provided utilizing individual usernames and passwords (adhering to DFMCH/UW Health password complexity policy) as well as an added two-factor authentication system. This will provide an extra layer of security for access into the system. The storage system will be housed in the DFMCH server facility, which is secured 24x7 and has limited access, and will provide full-disk encryption (at rest encryption) for all files.

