9.2.2 Missing Data

To minimize the extent of missing data, all surveys conducted electronically will be built to require a response for each question before proceeding. All non-electronic surveys will be double-checked for completeness by study personnel prior to conclusion of the assessment session. If missing data is discovered in a given participant's record after they have left the assessment session, the research coordinator will contact them by phone and attempt to collect the data within 14 days of the participant's assessment session.

The majority data at 3, 6 and 9 month follow-up visits is expected to be collected remotely, online or by phone. In cases where internet or phone access is not available, data may be collected by mail. The exit follow-up will be conducted in person when feasible. Data on main outcomes is planned to be collected at all assessments. Other survey-based data is planned to be collected at selected follow-up assessments and other contact times as outlined in Appendix. To minimize recall bias, subjects will be asked to keep a log of MM and CBT home practice, adverse effects, and opioid medication use with standardized data collection forms (see Appendix) and submit it by internet, phone or mail. We will design the study's RedCap database to send participants reminders about keeping track of the above data. We will call those unable or unwilling to use the online reporting and/or reminders.

We will implement statistical methods to assess for and minimize the impact of missing data (see Appendix).

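### The protocol body links no immediate response to a positive self-harm answer (COMM item 5 scored 3 or 4) entered in an online follow-up survey outside business hours.

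*Combined protocol and SAP*

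**What the plan says.** Section 11.1 (Medical/Safety Monitoring) screens for intent to self-harm at baseline and at 3, 6, 9 and 12 months with COMM item 5, which asks about frequency over the past 30 days. Scores of 3 (often) and 4 (very often) are a positive screen. Research staff then start the Safety Protocol and involve the designated study clinician. The paragraph ends by stating when answers are looked at: "COMM responses are monitored by the research staff during business hours".

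Follow-up surveys at 3, 6 and 9 months are done online or by phone. For the online route, Section 9.1 says "each participant will follow a unique web link (emailed to each participant at the time of follow-up) that will allow answering survey questions online". Section 9.3 encourages participants to try the link at the first visit, "so they can have practice with the web-link surveys prior to completing them remotely on their own". Section 9.2.2 adds that "all surveys conducted electronically will be built to require a response for each question before proceeding".

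On what a participant receives after a positive screen, Section 11.1 says: "All participants assessed by the study clinician will be provided information on the local resources available for counseling or other mental health services". Section 2.5.2 (Protection Against Risks) provides an on-call physician who can always be reached, an on-call mental health specialist able to deal with acute suicidality, and resource information as part of the Safety Protocol. It places the full Safety Protocol in an Appendix.

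**The concern.** The study asks the question, defines which answers are positive, and lets people answer with no staff present. A participant who reports late on a Friday that they often think seriously about self-harm would, under the stated rule, get neither information nor contact in response to that answer until staff next look at the data.

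This population makes such an answer foreseeable. Section 2.5.1 describes these patients as at raised risk of mental health problems. Section 5.3 deliberately does not exclude depression, anxiety or substance use disorders. Section 8.1 expects about 35% to have elevated negative affect. What is at stake is participant safety; no estimate, error rate or power figure is affected.

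**Working it through.** The plan gives no figure to reproduce. The check is a reading of the relevant sections together, followed by an illustration of the wait.

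**1. Can a positive answer arrive with no staff present?** Yes, at 3, 6 and 9 months. The link is personal, answers go straight into the database (Section 9.1), and participants are expected to complete the surveys alone (Section 9.3). No section restricts the time of day. Phone, in-person and live virtual assessments have a researcher present. The 12-month exit assessment is planned as a visit, with "Completion by phone or mail if necessary" in Table 4, so it is mostly outside this concern.

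**2. Will each completed online survey yield a screen result?** Yes. Electronic questions cannot be skipped (Section 9.2.2).

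**3. What in the body is triggered by the answer itself, before staff review?**

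| Provision | Section | What sets it in motion |
|---|---|---|
| Safety Protocol and clinician assessment | 11.1 | Staff reviewing the answer |
| Resource information | 11.1, 2.5.2 | Clinician assessment, the Safety Protocol, or staff noticing a problem |
| On-call physician and mental health specialist | 2.5.2 | A call from staff or participant |
| Information sheet naming a contact | 5.6.1 | The participant calling |
| Study phone numbers | 5.4.2 | The participant calling |
| Check-ins about every 2-4 weeks | 7.2.3 | The calendar, or engagement needs |
| Monitoring of electronic data | 11.4 | An assessment not being completed |

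None is linked to a 3 or 4 at the moment of entry. The body describes no on-screen message and gives no maximum review time.

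**4. How long could the wait be?** The documents do not define business hours. Assume Monday to Friday staffing of h hours a day, with review as soon as staff return.

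- Weeknight: 24 − h. For h = 8, 16 h; for h = 10, 14 h.
- Weekend: (24 − h) + 48. For h = 8, 64 h; for h = 10, 62 h.
- Three-day weekend: (24 − h) + 72. For h = 8, 88 h; for h = 10, 86 h.
- Unmonitored share of the week: (168 − 5h)/168. For h = 8, 128/168 = 76%; for h = 10, 118/168 = 70%.

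Later review lengthens each wait.

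**5. How many people would be affected?** This cannot be derived. The share answering online, the share answering out of hours and the rate of positive answers are all absent.

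**The case against.** The strongest objection is that the missing item is just the kind of detail the protocol keeps elsewhere. The Safety Protocol, data collection tools and consent form are all assigned to an Appendix, and a message triggered by one item would naturally sit in the survey tool. A reader might infer that the trial has no out-of-hours provision at all. The documents do not support that, because the Appendix was not available. This objection stands, and it limits the finding to the body.

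Second, the review hours are stated openly, and item 5 is a periodic screen with a 30-day look-back, not a crisis line. That also stands. There is no contradiction in the plan, and nothing here calls for round-the-clock staffing.

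Third, the safety cover is substantial. It includes an on-call specialist for acute suicidality, and Section 11.1 has a broader sentence promising resource information to anyone with mental health problems. Participants are therefore not without help. But that sentence follows text on sessions where a therapist or researcher is present, as does the reference to online platforms. The on-call cover is not connected to an unattended survey answer.

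Finally, a reader might take the volume of surveys (up to 800 × 3 = 2,400 at months 3, 6 and 9) as the scale of the problem. It is not. That ceiling ignores phone completion and counts surveys, not positive answers or out-of-hours entries.

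**Conclusion.** The point holds for the protocol body. Following Section 11.1 as written, a 3 or 4 entered online out of hours produces no information and no contact until staff review it, unless the participant makes the call. On assumed weekday staffing of 8 to 10 hours, the longest ordinary wait is about 62 to 64 hours, and 86 to 88 hours over a three-day weekend. Both ranges rest on that assumption and on prompt review when staff return.

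This is a modest safety improvement worth making, not an error in the design or analysis. Confidence is medium because the Appendix may already contain the response.

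**What to change.** First check the Safety Protocol and survey tools in the Appendix. If they already provide an immediate response, cross-reference it in Section 11.1. If not:

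- Program the online survey so that a 3 or 4 on item 5 at once displays crisis and local resource information and the existing study or on-call contact number.
- Add a line to the survey saying that answers are reviewed in business hours and that it is not an emergency channel. Section 11.1 already states the review hours.

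Keep the item, threshold, Safety Protocol and analysis unchanged. The cost is minor survey programming and an IRB amendment; the message needs no identifiers and no out-of-hours staff.

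Enclosing the same information with mailed surveys is a small optional extra. An automatic alert to the on-call clinician is not part of the recommendation and is best left to the sponsor. Outcome data carry only a study ID, and Section 2.5.2 says "A master list with identifiers will be kept in a separate secure database/separate locked filing cabinet" at the site's research office, so an alert would need new out-of-hours access to participants' identities.
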